January 2nd 2023

Effect of Biologics on Alternative Functions of Eosinophils in Severe Asthma

EudraCT: NCT04520165

Scientific Background and goal

Refractory asthma still represents between 3 to 10% of asthmatic patients. These patients represent a high burden in terms of healthcare costs. Biotherapies have been developed within the last years to reduce the use of oral corticosteroids (OCS), which are responsible for long-term and costly side effects. Monoclonal antibodies directed against interleukin (IL)-5 or its receptor (IL-5R) are approved to treat severe eosinophilic asthma with tangible improvements of the patient conditions. But it appears that the patients do not respond the same way to biotherapies.

In addition to the “super-response”, a new concept of asthma “remission” has recently emerged as a therapeutic target to achieve after 12 months of treatment and was defined according to results of randomized control trials (RCT) as obtaining asthma control, no exacerbation, no treatment with OCS while there is no consensus on the importance of improvement in lung function and reduction in type-2 (T2) inflammation in the current definition of remission.

Post-hoc analysis of RCT looked at the predictive factors of response to benralizumab or mepolizumab in vast cohorts of patients and observed that high blood eosinophil level was linked to a better improvement in terms of reduction of exacerbation rate. Even if blood eosinophils help to predict a general response to anti IL-5/ anti IL-5R, biomarkers reflecting local inflammation, such as those measured in induced sputum, have a better potential to predict the intensity of response to biologics as they reflect what really happens in the bronchi. So are there biomarkers of remission after therapy targeting IL-5 in the sputum of severe eosinophilic asthmatics? There are, to our knowledge, no studies analyzing inflammatory mediators as predictors of response after one year of anti-IL-5 treatment directly in the sputum itself in severe eosinophilic asthmatics. The goal of this paper is to analyze the role of mediators of the T2 cascade in the sputum as predictors of remission.

Study design and methods

Patients

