Fifty-two severe asthmatics initiated with an anti-IL-5 (51 with Mepolizumab and one with Reslizumab) were recruited from our asthma clinic. This observational study was performed at the CHU of Liege, Belgium, between 2014 and 2021. Inclusion criteria included a diagnosis of asthma defined by the Global Initiative for Asthma (<http://ginasthma.org/>), severe asthma was defined according to European Respiratory Society (ERS)/ American Thoracic Society (ATS) criteria. The treatment was stable for all patients at the time of the sampling and the time between baseline and the next evaluation was in average one year. Remission was defined as patients combining after the instauration of the biotherapy: no oral corticosteroids, no exacerbation, ACQ lower than 1.5 and/or asthma control test (ACT) greater than 19 and, a FEV₁ \geq 80% predicted and/or an improvement of FEV₁ \geq 10% and a blood eosinophil count lower than 300 cells/ μ l.

Sub-analyses were also performed to assess the predictive values of sputum mediators in terms of response for some specific parameters alone, such as: an improvement of ACT greater than 19 post-treatment, a decrease of ACQ lower than 1.5 post-treatment, a decrease of sputum eosinophil under 3% or by 50%, stopping OCS post-treatment, no more exacerbations post-treatment and improvement of FEV₁ of at least 10% post-treatment.

A diagnosis of nasal polyps by an Ear-Nose-Throat specialist and a diagnosis of atopic dermatitis or urticaria done by a dermatologist were reported.

This study was approved by the Ethics committee of CHU Liege (2005/181) and all subjects gave written informed consent for participation. The study ClinicalTrials.gov Identifier is clintrial.org EudraCT: NCT04520165.

Study design

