The normality of continuous variables was assessed by Shapiro-Wilk test (normal distribution was found for age, BMI, ACQ, AQLQ, pulmonary function parameters, fibrinogen level, and sputum neutrophil percentage). To investigate baseline characteristics of patients remission group, Chi-square or Fisher exact test was used for categorical variables and Student t test or Mann-Whitey U test was performed for continuous variables when appropriate.

Univariate logistic regression was considered to model the association between patient remission status and demographic, clinical and biological variables. Results of logistic regression were presented using odds ratios and corresponding 95% confidence interval.

All tests were performed 2-sided and $p < 0.05$ was considered significant. All statistical analyses were performed using SAS 9.4 (SAS Institute, Cary, NC), except for ROC curve calculation, GraphPad Prism 7 (GraphPad Software San Diego, CA, USA) was used. The p-values associated with the ROC curves tested the null hypothesis that the area under the curve equals 0.50.

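### Every sputum mediator analysis is unadjusted, so the plan cannot tell a mediator that adds information on remission from one that only marks baseline oral corticosteroid (OCS) use

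*Combined protocol and SAP*

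**What the plan says.** All references are to the combined protocol and SAP.

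- **Statistical analysis.** The regression is described thus: "Univariate logistic regression was considered to model the association between patient remission status and demographic, clinical and biological variables". For group comparisons, a Student t test or "Mann-Whitey U test was performed for continuous variables when appropriate". The ROC p-values "tested the null hypothesis that the area under the curve equals 0.50". No multivariable model, OCS stratum or OCS-free subgroup is named anywhere.
- **Patients, remission definition.** The required components begin "no oral corticosteroids, no exacerbation, ACQ lower than 1.5" and continue with lung function and blood eosinophils.
- **Patients, sub-analyses.** Single-component responses include "stopping OCS post-treatment, no more exacerbations post-treatment".
- **Patients, sampling.** "The treatment was stable for all patients at the time of the sampling". Patients are not required to be free of OCS when sputum is taken.
- **Scientific Background and goal.** Biotherapies are said to have been developed "to reduce the use of oral corticosteroids (OCS)". The stated goal is to assess sputum T2 mediators as predictors of remission.

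**The concern.** Baseline OCS use is tied to the outcome by definition. A patient who enters off OCS already meets that component and has only to stay off; a patient who enters on OCS must first stop. If OCS use also goes with the mediator level at sampling, an unadjusted comparison of remitters and non-remitters picks up part of the OCS contrast.

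This can act in either direction. If levels are lower in users, a high level looks predictive even with no link to remission among users or among non-users. If levels are higher in users, for example because their disease is more severe, a real predictor can be hidden.

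Stable treatment at sampling limits change within a patient; it does not remove the difference between users and non-users. Testing OCS as a separate univariate predictor does not remove it from any mediator result.

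At stake is what a reported mediator or ROC cut-off means. The clinician already knows OCS status, so a sputum assay is useful to the extent that it adds to it.

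**Working it through.** **1. The plan's own figures.** The Study design section gives 10-13 patients per group for 70-80% power at 5%, with no difference or SD. Using n = 2(z₀.₉₇₅ + z_power)²/d² and solving backwards, d = 1.12 gives 2(1.960 + 0.524)²/1.254 = 9.8, so 10 at 70% power, and 2(1.960 + 0.842)²/1.254 = 12.5, so 13 at 80%. The figures are consistent with a standardised difference of about 1.11-1.14. Expected remissions are 0.20 × 52 = 10.4, in line with the stated 10. Neither figure bears on adjustment, but they set the scale: about 10 events and effects near 1 SD.

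**2. Inputs for the check.** From the documents: n = 52, remission about 20%, two-sided 5%, and 11 mediators (EPX, IgE and nine by multiplex assay). Assumed, because the documents do not give them: share on OCS at baseline p = 30-50%; remission in users r₁ = 0-10%; mediator lower in users by d = 0.5-1.0 SD on a log scale; no mediator-remission link within either OCS group. Remission in non-users is r₀ = (0.20 − p·r₁)/(1 − p); for example p = 0.5 and r₁ = 0.05 give 0.35.

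**3. What the overall AUC becomes.** Let q₀ and q₁ be the shares of OCS users among non-remitters and remitters. With normal mediator values and no within-group link,

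AUC − 0.50 = (q₀ − q₁) × [Φ(d/√2) − 0.50].

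| p, r₁, d | q₀ | q₁ | AUC |
|---|---|---|---|
| 0.3, 0.10, 0.5 | 0.27/0.80 = 0.338 | 0.03/0.20 = 0.15 | 0.50 + 0.188 × 0.138 = 0.53 |
| 0.4, 0.05, 1.0 | 0.38/0.80 = 0.475 | 0.02/0.20 = 0.10 | 0.50 + 0.375 × 0.260 = 0.60 |
| 0.5, 0, 1.0 | 0.50/0.80 = 0.625 | 0 | 0.50 + 0.625 × 0.260 = 0.66 |

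The AUC stays at 0.50 if OCS is unrelated to the mediator (d = 0) or to remission (q₀ = q₁). It falls below 0.50 if users have higher levels.

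**4. How often the planned test flags such a mediator.** Simulation, 2,000-3,000 cohorts per scenario:

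| On OCS | Remission in users | Shift | Mann-Whitney p < 0.05 |
|---|---|---|---|
| 30% | 10% | 0.5 SD | 6.3% |
| 30% | 5% | 1.0 SD | 11.9% |
| 40% | 5% | 1.0 SD | 14-15% |
| 50% | 10% | 1.0 SD | 11.6% |
| 50% | 5% | 0.5 SD | 9.0% |
| 50% | 5% | 1.0 SD | 21.1% |
| 50% | 0% | 1.0 SD | 34-35% |

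Over the whole grid the range is about 5-35%, mostly 6-15%. A van Elteren test (Mann-Whitney stratified by OCS) rejects in 4-6%. In the scenarios with 5% or 10% remission in users and 30% or 50% on OCS, crude logistic regression rejects in 6.6-22.8%, and in 5.5-7.0% once baseline OCS is in the model.

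**5. The opposite direction.** With a true 1 SD predictor and levels 0.7 SD higher in users, power is about 46-48% unstratified and 70-71% stratified.

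**6. Price of adjusting when it is not needed.** With a true 1 SD effect and no OCS-mediator link, power goes from 0.76 to 0.74 in mild scenarios, from 0.78 to 0.71 with 40% on OCS and 5% remission in users, and from 0.77 to 0.68 with 40% on OCS and no remission in users. The loss is about 3-13 points over the grid. One set of runs gave 15 points (0.75 to 0.60) with 50% on OCS and no remission in users, the same corner that produces the 35%.

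**The case against.** The strongest reply is that the goal is prediction, not causation. A mediator that marks OCS use does discriminate remitters from non-remitters in the whole cohort, so a test of AUC = 0.50 that rejects is right about its own null hypothesis. This stands. A reader might infer from the simulation that up to 35% of flagged mediators would be false positives; the documents do not support that. The rates show how often a mediator with no information beyond OCS would be reported, which is a narrower statement.

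It is also true that the key inputs are absent. Nothing in the documents says that OCS lowers sputum mediators, how many patients used OCS, or how remission differed by use. The stopping-OCS item implies some users, not a number.

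Part of the plan helps. The sub-analyses on ACT, ACQ, FEV₁, sputum eosinophils and exacerbations do not contain the OCS component, so the built-in link is absent there, although differences in severity between users and non-users can remain. Stopping OCS can apply only to baseline users, so it is in effect a within-user analysis. The planned group comparisons could also show an OCS imbalance. None of this separates OCS from the mediator in the main remission analysis.

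Finally, about 10 remissions support little adjustment, a yes/no term ignores dose, and a stratified test gains nothing from a stratum with no remitters. These points limit the adjustment to one binary term and argue against letting it replace the planned analysis.

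**Conclusion.** The point holds in a limited form. Two facts come from the documents: every named mediator analysis is unadjusted, and freedom from OCS is built into remission in a cohort that appears to include baseline users. It follows that the plan cannot show whether a mediator adds to known OCS status, and cannot reveal one that OCS use masks.

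The size is not known. It runs from negligible, if OCS is unrelated to either the mediator or remission, to about 35% of cohorts flagged, and that top figure needs 50% on OCS, a full 1 SD shift and no remission in users all at once. Most assumed scenarios give 6-15%.

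A reader might go further and conclude that OCS is known to suppress these mediators here, or that the univariate results are invalid and should be reduced to description. The documents support neither: the first is an assumption of uncertain direction, and the univariate results answer a legitimate marginal question.

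**What to change.** Keep the planned univariate results and add, for each mediator, a co-reported analysis adjusted for baseline maintenance OCS (yes/no):

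- a van Elteren test stratified by that term;
- a logistic model with the mediator plus that one term, using Firth or exact estimation if a cell is empty;
- the ROC curve in patients not on OCS at baseline, beside the overall curve;
- a table of baseline OCS use by remission group.

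Describe a mediator as predicting remission beyond known OCS status only where the adjusted result supports it.

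**Cost.** A few lines of SAS and no new patients or assays. Baseline OCS status should already be available, because the stopping-OCS sub-analysis needs it. The statistical price is the power loss shown above, about 3-13 percentage points for a 1 SD effect when OCS is unrelated to the mediator. It is largest when no OCS user remits, because that stratum then contributes nothing. With 30-50% on OCS, the ROC curve in non-users would rest on about 26-36 patients (52 × 0.5 to 52 × 0.7), so it should be shown with its confidence interval.

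### Eleven sputum mediators are each judged against remission at an unadjusted p<0.05, with no primary mediator, exploratory label or deciding test; in an illustrative scenario the chance of at least one false predictor is about 12–35%

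*Combined protocol and SAP*

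**What the plan says.** Scientific Background and goal states the aim for the mediators as a set: "The goal of this paper is to analyze the role of mediators of the T2 cascade in the sputum as predictors of remission". The section on sputum mediator measurement lists 11: EPX and IgE by ELISA, and IL-3, IL-4, IL-5, IL-13, IL-25, IL-33, GM-CSF, TSLP and eotaxin-1 by multiplex assay.

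The Statistical analysis section gives one threshold for everything: "All tests were performed 2-sided and $p < 0.05$ was considered significant". It describes three ways in which a mediator can be set against remission status:

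- a group comparison, where "Student t test or Mann-Whitey U test was performed for continuous variables when appropriate";
- a regression: "Univariate logistic regression was considered to model the association between patient remission status and demographic, clinical and biological variables";
- ROC curves, whose p-values "tested the null hypothesis that the area under the curve equals 0.50".

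It does not say which of these decides that a mediator is a predictor, and it mentions no multiplicity adjustment. IL-5 appears in Study design only as the basis of the sample size, not as a primary mediator. The Patients section adds more tests under the same rule: "Sub-analyses were also performed to assess the predictive values of sputum mediators in terms of response for some specific parameters alone".

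**The concern.** When 11 candidates are each tested at 5% and every significant one may be called a predictor, the error rate that matters is that of the list. Naming predictors is the paper's stated goal, so a false entry on the list is an error in its main conclusion. Nothing in the text tells the reader to treat the mediator results as a screen, and the powered sample-size statement points the other way.

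No treatment decision in this study depends on the result. What is at stake is what the study can claim, and any later work built on a marker that was significant by chance.

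**Working it through.** **Inputs from the documents.** 52 patients; at least 10 expected in remission, hence about 10 against 42; 11 mediators; two-sided 0.05 throughout.

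**Inputs assumed.** Only IL-5 truly differs and the other ten are null. The mediators are equally correlated, at 0.3 to 0.7. The effect size is back-solved in step 1.

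**Step 1: the plan's own figure.** Study design gives 10–13 per group for 70–80% power at 5%, without an effect size, so it cannot be reproduced from stated inputs. Solving d = (1.96 + z_power) × √(2/n):

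- n = 10, 70% power: (1.96 + 0.524) × √0.2 = 1.11 SD
- n = 13, 80% power: (1.96 + 0.842) × √(2/13) = 1.10 SD

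The range is consistent with one difference of about 1.1 SD, which I use below.

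**Step 2: which test.** The variables reported as normal are these: "normal distribution was found for age, BMI, ACQ, AQLQ, pulmonary function parameters, fibrinogen level, and sputum neutrophil percentage". No sputum mediator is among them, so Mann-Whitney is the likely group test. The AUC is U/(n1 × n2), so the test of AUC = 0.50 assesses the same quantity and is not separate evidence. Logistic regression is the other real candidate.

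**Step 3: uncorrelated bound.** With ten null mediators, 1 − 0.95^10 = 40%. The exact Mann-Whitney size at 10 against 42 is 0.0487, which gives 1 − 0.9513^10 = 39%.

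**Step 4: simulation with correlation.** 10 against 42, IL-5 shifted by 1.1 SD, ten null. The logistic column uses Wald tests on log-normal markers (log-SD 1, assumed).

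| Correlation | At least one false, Mann-Whitney | At least one false, logistic | IL-5 and a false one both named, Mann-Whitney |
|---|---|---|---|
| 0.3 | 35% | 19% | 29% |
| 0.5 | 29% | 16% | 23% |
| 0.7 | 22% | 12% | 15–16% |

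Repeat runs agree to about one percentage point. The logistic rates are lower because the Wald test is conservative here, with a per-test error of about 2.2–2.5%. Over correlations from 0 to 0.9 the Mann-Whitney rate runs from 39% to 14%. With 13 remitters against 39 it is 35% at 0.3 and 22% at 0.7.

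**Step 5: with adjustment over all 11** (Mann-Whitney, correlation 0.3 to 0.7). The chance of at least one false predictor falls to about 3–4% with Holm and about 4–7% with Benjamini-Hochberg. If the adjusted threshold decided, power for one true mediator at 1.1 SD would fall from about 84% to about 52%. With Benjamini-Hochberg it would be 58% if two mediators were truly associated and 63% if three.

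**The case against.** **The figure depends on a test that the plan does not choose.** This stands. The plan ties the group tests to baseline characteristics and logistic regression to association with remission, so regression is at least as natural a deciding test. That is why the range is 12–35% and not the Mann-Whitney range alone.

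**IL-5 alone being associated is my scenario, not the plan's.** This also stands. The documents never say that ten mediators are null. All 11 are presented as parts of one inflammatory cascade, and the rate falls if more of them are truly associated.

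**The lack of a deciding test adds little by itself.** Largely right. Counting a mediator if either Mann-Whitney or logistic regression is significant gives a per-mediator error of only 5.4–6.1%. A reader might infer that three tests triple the error; they do not, since two of them assess the same quantity.

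**A false marker would look as good as a real one.** A reader might infer this, but the figures do not support it as the usual outcome. The smallest significant AUC at 10 against 42 is 295/420 = 0.70, whereas a true 1.1 SD difference corresponds to about Φ(1.1/√2) = 0.78. In this scenario a significant null marker equals or beats IL-5's AUC in about 8–11% of studies.

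**Values below detection limits might change the result.** With 50–70% of values tied, the Mann-Whitney rate is still 24–35% at correlations of 0.7 to 0.3.

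**Adjustment is costly in a small observational study.** This is fair as an argument against letting the adjusted threshold decide alone. It is no argument against showing the adjusted p-value or labelling the analyses.

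**Conclusion.** The concern holds. The documents apply an unadjusted 5% rule to each of 11 mediators, aim to name predictors among them, and give neither a primary mediator nor an exploratory label. That much rests on the text alone.

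The size rests on assumptions: 10 remitters, IL-5 alone different by 1.1 SD, and correlations of 0.3 to 0.7. The chance of at least one false predictor is then about 12–35%, depending on the deciding test. The chance that IL-5 and a false mediator are both named is about 29% to 15–16% by Mann-Whitney. These figures cover one test per mediator against remission. They leave out the demographic and clinical variables and the single-parameter sub-analyses, whose number the documents do not give.

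A reader might go further and infer that individual p-values are invalid or that any named mediator is probably false. The documents support neither. The fault lies in how a list of significant mediators may be described, and it should be fixed in the reporting.

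**What to change.** For the 11 mediators against remission:

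1. Use one test per mediator. Mann-Whitney fits, since the mediators are not among the variables reported as normal.
2. Do not present the p-value for AUC = 0.50 as evidence separate from Mann-Whitney.
3. Keep the unadjusted p-values, AUCs and odds ratios with 95% confidence intervals, and add beside them a Benjamini-Hochberg adjusted p-value over all 11.
4. Label the mediator analyses and the single-parameter sub-analyses exploratory, and state how many tests were made.
5. Describe mediators that are significant only before adjustment as candidates that need confirmation.
6. State that the adjustment was added after data collection. Patients were studied "between 2014 and 2021", the document is dated January 2023, and it already reports normality results. The adjustment therefore limits the claim but does not make it confirmatory.

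The cost is wording, one extra column and a more cautious claim; no new data are needed. Because of the power loss if the adjusted threshold decided alone, the unadjusted results stay in the report. If no adjustment is wanted, exploratory labelling with the test count is an adequate minimum.

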This study aims to investigate the airway expression of mediators of the T2 cascade as predictors of remission after anti-IL-5 treatment in a cohort of patients with severe eosinophilic asthma. To detect a difference between groups with a power of 70-80% and a significance level of 5%, the sample size was estimated as 10-13 patients per group (<https://www.sealedenvelope.com/>). These calculations were based on a significant difference of sputum IL-5 obtained as preliminary results. Usually, in the different studies, even if there is no consensus on the remission definition in the asthma context, there is mention of a percentage around 20% of patients exhibiting a good response to anti-IL-5. Consequently, with a cohort of 52 patients, we expected a sample size of at least 10 patients in the remission group.

Respiratory function

FeNO was measured using NiOX (Aerocrine, Solna, Sweden) at a flow rate of 50 mL/s. Spirometry was performed before and after bronchodilation according to the ATS/ERS standard criteria.

Blood samples

Blood samples of patients were analyzed by the routine laboratory of the University Hospital of Liege for leukocyte count, c reactive protein (CRP) and fibrinogen levels.

Sputum induction and processing.

The sputum was induced and processed as previously described and the sputum supernatant was collected before the addition of dithiothreitol (DTT), which could impact the measurements. Cell viability was determined by trypan blue exclusion and the differential cell count was performed by counting 500 non-squamous cells on cytospins stained with May-Grünwald-Giemsa.

Sputum inflammatory mediators measurement

Eosinophil peroxidase (EPX) was measured by classic ELISA (Mybiosource, CA, USA). Detection limit was 5.4 ng/ml. Immunoglobulin E (IgE) levels were measured with Human IgE ELISA kit from Abcam (Amsterdam, Netherlands). The detection limit was 30.5 pg/ml. Finally, interleukin (IL)-3, IL-4, IL-5, IL-13, IL-25, IL-33, granulocyte-macrophage colony-stimulating factor (GM-CSF), thymic stromal lymphopoitin (TSLP) and eotaxin-1 were measured by multiplex electrochemiluminescent assays (Meso Scale Discovery). This technic was already used with success in sputum supernatant in the past and spiking recovery were optimal.

Statistical analysis

Categorical variables are presented as numbers and percentages, continuous variables are presented as mean \pm standard deviation or as median (interquartile range P25-p75) when appropriate.

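### Does the plan need to specify a 95% interval for the ROC areas, given that it states only a p-value against 0.50 and expects about 10 of 52 patients in remission?

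*Combined protocol and SAP*

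**What the plan says.** The Scientific Background and goal section frames the study as one of prediction: "The goal of this paper is to analyze the role of mediators of the T2 cascade in the sputum as predictors of remission".

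The Study design section justifies the size by a comparison of groups. For 70-80% power at the 5% level, "the sample size was estimated as 10-13 patients per group", and "These calculations were based on a significant difference of sputum IL-5 obtained as preliminary results". The difference, its standard deviation, the test and the allocation ratio are not given. From a response share of around 20%, the section concludes that "with a cohort of 52 patients, we expected a sample size of at least 10 patients in the remission group".

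The Statistical analysis section covers two kinds of association result. For the univariate logistic models, "Results of logistic regression were presented using odds ratios and corresponding 95% confidence interval". For the ROC curves it gives the software ("except for ROC curve calculation, GraphPad Prism 7 (GraphPad Software San Diego, CA, USA) was used") and the meaning of the p-value ("The p-values associated with the ROC curves tested the null hypothesis that the area under the curve equals 0.50"). It does not say which outcome the curves use, and it neither promises nor rules out an interval for the AUC.

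**The concern.** A test against 0.50 asks whether a mediator separates the two groups at all. A claim that a mediator predicts remission depends on how well it separates them, and that is read from the AUC and its interval. With about 10 patients in the smaller group, a small p-value can sit beside an AUC whose plausible values run from little better than chance to very good. The same section commits to intervals for odds ratios, so their absence for the AUC looks like an oversight on the measure closest to the study's aim.

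The choice of interval also has some effect at this size, because a symmetric interval under-covers. At stake is how firmly a reader could take the phrase predictor of remission if the published result were a p-value alone.

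**Working it through.** **Inputs from the plan.** 52 patients; around 20% responding; 10-13 per group; 70-80% power; two-sided 5%. No AUC, IL-5 difference or standard deviation is given, so every AUC below is an assumption.

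**The plan's own figures.**
- Expected remissions: 0.20 × 52 = 10.4, which agrees with at least 10 as an expectation and leaves 42 not in remission.
- The 10-13 per group cannot be computed forwards without an effect size. Solved backwards with d = (1.96 + z_power) × √(2/n):
  - n = 10 at 70% power: (1.96 + 0.524) × √0.2 = 1.11
  - n = 13 at 80% power: (1.96 + 0.842) × √(2/13) = 1.10
- Both ends of the range fit one standardised difference of about 1.1, so the statement is coherent.
- Under equal-variance normality that d gives AUC = Φ(1.1/√2) = 0.78. This serves as one working value. Sputum IL-5 is not among the variables the plan lists as normally distributed.

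**Test against 0.50.** Null SE = √((m + n + 1)/(12mn)). For 10 v 42: √(53/5040) = 0.1025. An observed AUC of about 0.50 + 1.96 × 0.1025 = 0.70 is therefore on the edge of significance. At 0.78, z = 0.28/0.1025 = 2.73 and p = 0.006.

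**Precision.** Hanley-McNeil: SE² = [A(1−A) + (m−1)(Q1−A²) + (n−1)(Q2−A²)]/(mn), with Q1 = A/(2−A) and Q2 = 2A²/(1+A). At A = 0.78, Q1 = 0.6393 and Q2 = 0.6836. The formula rests on exponential distributions, and the result depends on whether the remission group has the higher or the lower values; both are shown. Symmetric interval: A ± 1.96 SE. Logit interval: logit(A) ± 1.96 × SE/[A(1−A)], transformed back.

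| Groups | Assumed AUC | p | SE (two shapes) | Symmetric 95% | Logit 95% |
|---|---|---|---|---|---|
| 10 v 42 | 0.70 | 0.051 | 0.100 / 0.084 | 0.50-0.90 / 0.53-0.87 | 0.48-0.86 / 0.52-0.84 |
| 10 v 42 | 0.78 | 0.006 | 0.092 / 0.071 | 0.60-0.96 / 0.64-0.92 | 0.55-0.91 / 0.61-0.89 |
| 10 v 42 | 0.90 | 0.0001 | 0.067 / 0.044 | 0.77-1.03 / 0.81-0.99 | 0.67-0.98 / 0.78-0.96 |
| 13 v 39 | 0.78 | 0.003 | 0.082 / 0.067 | 0.62-0.94 / 0.65-0.91 | 0.58-0.90 / 0.62-0.88 |

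**Coverage.** In simulations with 10 v 42, a true AUC of 0.78 and the DeLong variance (20,000 runs for each of three distribution shapes), nominal 95% intervals covered the true value in 89-92% of runs on the symmetric scale and 93-95% on the logit scale.

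**What this shows about the plan.** The AUC will be imprecise, and a logit-type interval behaves better than a symmetric one at this size. Neither result contradicts anything written. The plan names no symmetric interval, sets no precision target that it misses, and does not present the p-value as a measure of predictive strength. The extra quantities need only each curve's data and group counts, so leaving them unspecified closes off nothing.

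**The case for a change.** The strongest case for a change is that the gap is cheap to close and lies on the central measure. Two or three sentences would commit the authors to an AUC with its interval, a method and the group counts, as they already commit for odds ratios. Without that, a curve with p = 0.006 could be published with nothing to show that an AUC near 0.55 or 0.61 is also compatible with the data. An odds-ratio interval does not fill this role, because it does not measure discrimination.

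All of that stands as advice on reporting, and the calculations behind it reproduce. It does not show a fault in the plan:

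- Asking for an interval to be written down differs from finding a stated method that would mislead. The document is short and written largely in the past tense about a cohort studied from 2014 to 2021. An AUC interval can be added in the report without any amendment.
- Quoting only 0.55-0.91 overstates the case. It is the wider of two shapes at one assumed AUC. In the other shape, the gap between the lower limits of the symmetric and logit intervals falls from 0.05 to 0.03.
- Logit-scale DeLong is not the only sound choice. A stratified bootstrap would also serve, so prescribing one method is not needed.
- The ROC outcome is inferred. The curves may also serve the single-parameter sub-analyses listed under Patients, so a rule confined to remission curves would be arbitrary.
- The unstated inputs to the IL-5 calculation are a separate matter. Supplying them would say nothing about the precision of an AUC.

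**Conclusion.** No change to the plan is called for. The observation is accurate: an AUC interval is not specified, and with about 10 v 42 patients its logit-scale 95% limits would be roughly 0.28 to 0.36 apart at an assumed AUC of 0.78 (0.89 − 0.61 to 0.91 − 0.55). But the test against 0.50 is sound, the 10-13 per group is coherent with a single effect size, at least 10 matches 20% of 52, and no AUC, odds ratio or p-value would differ. What remains is a reporting detail that a competent analyst would supply with the results.

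The sizes quoted rest on assumed AUCs of 0.70 to 0.90, on 10 (or 13) remissions as an expected rather than observed count, and on the two exponential shapes used for the standard error. The conclusion does not depend on those values, because at any of them the interval could be added from the existing data.
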